3.1 Trial objectives

The aim of this trial is to study the long-term impact of multimodal treatment (chemotherapy, radiotherapy and surgery) in adult brain and base of skull tumours on neurocognitive functioning using neuropsychological testing combined with advanced MR imaging techniques in a multicenter observational cohort study. We differentiate two main objectives.

The first objective is to build an NTCP model for neurocognitive decline after RT (for each cognitive domain separately), linking dose-volume parameters to structures within the brain susceptible to neurological damage and neurocognitive decline after radiotherapy. These NTCP models will be used to make predictions on neurocognitive decline in future primary brain tumour patients receiving cranial RT. It will provide us with a much needed, evidence-based tool to select the optimal treatment modality for each individual patient and enables us to tailor cranial irradiation towards neurocognition-sparing treatment in the future.

The second objective is to evaluate dose-dependent neurocognitive decline. In particular, we will investigate:

- Prevalence and severity of neurocognitive decline after RT for all cognitive domains
- Brain structures or functional brain connections important in neurocognitive functioning (based on dedicated MRI).
- Dose-dependencies of specific neurocognitive skills after RT in adult brain tumour patients
- Correlations between RT dosimetry and early brain changes (MRI)

With this prospective observational trial, we aim to map the neurocognitive side effects of the irradiation treatment in cranially irradiated patients and the clinical and dosimetrical factors that play a role. Based on these findings, we plan to set up future prospective trials to validate these findings.

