3.2 Primary endpoints

- Predict neurocognitive decline based on RT dosimetric and other explanatory variables like gender, age at diagnosis, comorbidities, level of education, social factors such as social activity and occupation, tumour size and localization, pathological/genetic/molecular characteristics, therapy protocols (surgery, radiotherapy and/or chemotherapy) in an NTCP model for each cognitive domain
- Measure the prevalence and severity of neurocognitive decline compared to baseline at one year, for all cognitive domains (attention, memory, working memory, information/visuomotor processing speed, executive functioning)

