3.4 Trial Design

This is an observational cohort study which evaluates primary brain tumour patients longitudinally at the following timepoints: baseline (minimal 4 weeks after surgery (if indicated), before radiotherapy), three months (+/- 2 weeks) after end of radiotherapy, 1 year after end of radiotherapy (+/- 1 month) and 2 years after end of radiotherapy (+/- 1 month). At each visit, neurocognitive testing, a self-report inventory and/or advanced MR imaging will take place. During and after radiotherapy and at each follow-up visit, adverse events will be monitored using CTCAEv5.0²⁰.

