5.2 Neurocognitive assessment

We will perform a standardized neurocognitive test battery in all patients at baseline (prior to RT) and each consecutive year (1 year and 2 years post-RT). The acquisition of neurocognitive assessments takes approximately 1 hour. Results will be followed over time and compared to normative data ^{21,22}.

All these tests and questionnaires have been extensively described and used to quantify neurocognitive functioning in adults. Both neurocognitive testing and completion of the questionnaires takes place in the hospital.

We will use a broad evaluation of neurocognitive performance.

- The Montreal Cognitive Assessment (MOCA), is a screening instrument for cognitive deficits in multiple domains²³.
- Trail Making Task (TMT)²⁴, is an executive task which requires to link characters and digits in the correct sequence.
- Digit span (subtest of the Wechsler Adult Intelligence Scale(WAIS))²⁵ is a working memory task, which requires to repeat digits in same, reversed and sequencing order.
- The Hopkins Verbal Learning Test- Revised (HVLT-R)²⁶ is a verbal memory task for which participants need to repeat 12 words (three repetitions of free-recall) to assess verbal learning. Afterwards, they are asked to repeat or recognize the memorized words (Delayed recall and recognition).
- Controlled Word Association Test (COWAT)²⁷ assesses categoric and phonemic fluency. The participant is required to make verbal associations to a category or different letters of the alphabet by saying all the words which they can think of in this category or beginning with a given letter.
- The Stroop Color and Word Test (SCWT)²⁸ assesses the ability to inhibit cognitive interference that occurs when the processing of a specific stimulus feature impedes the simultaneous processing of a second stimulus attribute.
- The digit symbol substitution test of the WAIS (coding)²⁹ measures processing speed. This test consists of digit-symbol pairs followed by a list of digits. Under each digit the subject

should write down the corresponding symbol as fast as possible. The number of correct symbols within the allowed time is measured.

Cognitive domain	Neurocognitive test	Outcome measurement time				
Attention	TMT B					
Memory	HVLT immediate recall	Sum score - learning				
	HVLT delayed recall	Sum score				
	HVLT recognition	Good recognition-mistakes				
	WAIS IV digit span forward	Total number of series				
Executive functioning	COWAT	Sum of words				

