5.4 MRI imaging

We will perform an advanced MR protocol in every patient. No gadolinium contrast will be administered. Advanced MRI will be performed in all patients prior to RT (baseline), at three months, and at one year post-RT. All subjects will be imaged on the same scanner in each center (UZ Leuven: 3T Philips with a 32-channel phased-array head coil, located in the radiology department at UZ Leuven). Phantom scans will be used to adapt each protocol in every center. Neuroimaging will consist of:

- 3D high-resolution T1-weighted magnetization-prepared rapid acquisition gradientecho (MPRAGE) anatomical scan for grey/white matter volumetry
- o 3D T2-weighted FLAIR to examine leukoencephalopathy
- Advanced diffusion weighted- imaging (DWI). DWI is a technique enabling the visualization and characterization of the WM architecture via the self-diffusion of water molecules allowing us to study potential therapy-induced changes in the WM microstructure. Damage to WM structures for example axonal loss or demyelination may change quantitative DWI parameters such as fractional anisotropy (FA), mean diffusivity (MD) and diffusion kurtosis.
- Resting state functional MRI (rfMRI) to estimate neuronal activity of the brain at rest (examination with eyes closed). rfMRI uses the vascular response nearby electrically active neurons to indirectly visualize brain activity and allows us to determine the functional coherence (or so-called "connectivity") between the different brain regions at rest. Participants will therefore be asked to close their eyes during the examination, but not to fall asleep.
- Susceptibility-weighted MR imaging (SWI) to detect radiation therapy-induced cerebral microbleeds.
- Arterial Spin labeling (ASL) to measure tissue perfusion.

The duration of the proposed scan protocol is maximum 60 minutes.

6. Assessment of Safety

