7.2.1 Neuropsychological data

The following research questions are addressed by using multiple statistical tests.

- 1. How severe is the neurocognitive decline after treatment and how does it change over time?
- 2. Which neurocognitive domains are affected in which patients?

The first question is addressed by investigating the neurocognitive performance of primary brain and base of skull tumour patients. The performance on neurocognitive measures of the patients will be assessed at 3 timepoints over time. The raw test-scores are converted to normalized zscores based on normative data for each cognitive test. For each cognitive test, cognitive impairment is defined as a z-score \leq 1.5, and patients will be dichotomized according to their impairment status (impaired versus unimpaired). The frequency of impairment will be reported as descriptive information.

We will assess the evolution in the z-scores with a mixed repeated measures model to test changes throughout time. However, if the data are not normally distributed, the Friedman test will be used as alternative approach. The effects of the patient- and treatment-related predictors on the neuropsychological and questionnaire scores will be investigated using general linear models (predictors= tumour location, radiation dose, covariates= gender, age at treatment, time since treatment and socio-economic status) at each timepoint. Bonferroni correction will be applied as

method for statistical correction of multiple tests, for each test outcome (n=5 outcomes; memory, executive functioning, attention, visuomotor function, working memory) that is predicted.

Effect sizes of the tests will be reported. Partial eta squared (hp2) will be computed to estimate effect sizes (weak effect: $np^2 \approx 0.03$; moderate: $np^2 \approx 0.06$; large: $np^2 \geq 0.14$) for linear relationships between predictor and each outcome (e.g. age, time since treatment). Cohen's d will be used to estimate effect sizes for subgroup differences (small effect: 0.2 < d < 0.3; medium: 0.3 < d < 0.8; large: d > 0.8).

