7.2.2 Imaging

State of the art image analysis approaches are applied to process and analyze the acquired brain images and to document individual changes in structural white matter or resting state brain activity. Structural MRI data will be analyzed via voxel based morphometry (VBM) in Statistical Parametric Mapping (SPM). Multiple validated toolboxes will be used (e.g. FreeSurfer, ANTs, CAT12). To correct for distortions caused by the brain tumour itself, Virtual Brain Grafting will be used⁴⁵. DWI images will be processed and analyzed using MRtrix 3.0. Seed-based analysis and independent component analysis (ICA) will be applied to analyze the resting state fMRI data. The association between the obtained MR parameters and the performance on neurocognitive tests will be investigated using (voxel- and region of interest-based) correlation analyses. The independent effects of the predictors (radiation dose, gender, age at treatment, duration of treatment and socioeconomic status) on these neuropsychological test scores and imaging feature values will be analyzed with a (voxel-based) general linear model. For the MR analyses, repeated measures ANOVA will be conducted voxel-based to analyze the within-subject variability in tissue probability maps throughout time (e.g. grey matter or white matter volume, grey matter density, white matter microstructure). The significance threshold will be set at p < 0.05 false discovery rate (FDR) corrected for multiple comparisons.

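### The 1- and 2-year dose models list neither the pre-RT score nor centre, so they relate dose to current level rather than to decline, and they lose precision

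*Protocol*

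**What the plan says.** Section 7.2.1 of the protocol names the dose model for the test and questionnaire scores. Tumour location and radiation dose are the predictors; the rest of the model is "covariates= gender, age at treatment, time since treatment and socio-economic status) at each timepoint". On the number of occasions the section says: "The performance on neurocognitive measures of the patients will be assessed at 3 timepoints over time". Section 5.2 places them "at baseline (prior to RT) and each consecutive year (1 year and 2 years post-RT", and section 3.4 sets the follow-up visits at "1 year after end of radiotherapy (+/- 1 month) and 2 years after end of radiotherapy (+/- 1 month".

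The same section plans a mixed repeated measures model for the course of the z-scores. Baseline is one of its timepoints, but no dose term is named.

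On the aim, section 3.1 says: "The second objective is to evaluate dose-dependent neurocognitive decline". One primary endpoint in section 3.2 is: "Measure the prevalence and severity of neurocognitive decline compared to baseline at one year, for all cognitive domains".

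For imaging, section 7.2.2 plans a further general linear model, of test scores and imaging features: "The independent effects of the predictors (radiation dose, gender, age at treatment, duration of treatment and socioeconomic status". Baseline value, tumour location and centre are not in that list. Section 5.4 says: "All subjects will be imaged on the same scanner in each center". That secures one scanner within a centre, and section 7.1 names three recruiting centres.

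**The concern.** A model of the 1-year score on dose, without the pre-RT score, asks whether patients with a higher dose score lower at 1 year. It does not ask whether they have lost more since before RT. Patients with a brain tumour may already differ in cognition before RT, and the measurement that separates the two questions is scheduled for every patient.

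Two things are at stake. The first is precision: stable differences between patients stay in the residual and widen the interval around the dose coefficient. The second is interpretation: if dose goes with pre-RT deficit for reasons the listed covariates do not capture, part of that deficit is credited to dose.

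The listed time covariate does not help. Within one visit, time since RT is almost the same for everyone, and at the pre-RT visit neither it nor a delivered dose exists.

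**Working it through.** **1. The plan's own sample size.** Section 7.1 gives d = 0.368 and d = 1.271, two-sided alpha 0.05, power 0.80, and arrives at 8 to 60 patients. A paired t-test (noncentral t with n − 1 df, noncentrality d√n) reproduces this:

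- d = 0.368: n = 60 (power 0.801); at n = 120 the power is 0.979, as stated.
- d = 1.271: n = 8 (power 0.867; the protocol prints 0.868).
- A comparison of two independent groups would need 234 and 22 patients in total, so it is not what was done.

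The planning figure thus rests on within-patient change, the pairing that the per-timepoint dose models leave out.

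**2. Does another dose analysis bring baseline in?**

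- Section 7.2.1, mixed model: baseline yes, dose not stated.
- Section 7.2.2, general linear model: dose yes, baseline not listed. Repeated measures ANOVA: time yes, dose not stated.
- Section 7.2.3: univariate logistic regression of impairment status on dose, so no baseline.
- Section 7.2.4: the list of clinical variables has no baseline score.

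No dose analysis is stated to adjust for the pre-RT score.

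**3. Precision.** Let r be the correlation of baseline with follow-up score that remains after the other covariates. The documents give no value; 0.5 to 0.7 is assumed. Adding baseline multiplies the residual variance by 1 − r².

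| r | 1 − r² | SE factor √(1 − r²) | Unadjusted patients worth 120 adjusted: 120/(1 − r²) |
|---|---|---|---|
| 0.5 | 0.75 | 0.87 | 160 |
| 0.7 | 0.51 | 0.71 | 235 |

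The ratios are 1/0.75 = 1.33 and 1/0.51 = 1.96. In a simulation (n = 120, 1,500 data sets per setting, alpha 0.05, assumed standardised dose effect −0.20, dose unrelated to baseline), power rises from 0.542 to 0.680 at r = 0.5 and from 0.535 to 0.822 at r = 0.7.

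**4. Possible bias.** Let ρ be the correlation of dose with baseline score that remains after tumour location and the other covariates. It is also not given. In standardised units the dose coefficient without baseline is off by r × ρ:

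- ρ = 0: no bias.
- ρ = −0.1, r = 0.5: −0.05.
- ρ = −0.3, r = 0.7: −0.21.

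In simulation the last case gives a mean estimate of −0.413 without baseline and −0.202 with it, against a true −0.20. The SE is 0.092 without and 0.071 with baseline, so adjustment still gains precision when dose and baseline are correlated.

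**5. Time since RT.** The visit table in section 5.1 allows ±4 weeks. If visits are spread evenly over that window, the SD is 4/√3 = 2.3 weeks, or 2.3/52 = 4% of the interval at 1 year. One uninformative covariate raises the SE by √[(n − k − 2)/(n − k − 3)] − 1. With n = 120 and k = 10 other terms this is √(108/107) − 1 = 0.5%.

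**The case against.** A reader might infer that the dose effect is biased as planned, with a high false-positive rate. The documents do not support that. Tumour location, an obvious link between dose and pre-RT deficit, is already in the section 7.2.1 model. When the whole dose–baseline correlation is simulated as running through location, with no RT effect, the model without baseline rejects in 4–6% of trials. If a correlation of 0.3 with worse baseline remained after location and r were 0.7, it would reject in about 60% at alpha 0.05, and in about 35–40% at the 0.01 that Bonferroni over five outcomes implies (0.05/5). Nothing in the protocol says which case is nearer.

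Nor is baseline adjustment a complete cure. If dose goes with true ability and both scores carry measurement error (reliability 0.7, observed correlation 0.3), the adjusted model still rejects in about 30% of trials without an RT effect. Over reliability 0.5–0.8 and correlation 0.2–0.4 it rejects in 12–80%, and the unadjusted model in 59–99%. Adjustment helps, but the choice between it, change scores and a dose-by-time term can be argued in a non-randomised cohort.

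A reader might also infer that time since treatment wastes precision. It does not: the cost is about 0.5% of the SE. The protocol does not define the starting point either; counted from surgery or chemotherapy, the interval could vary more.

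Scanner differences do not bear on test and questionnaire scores; they belong to section 7.2.2. There, whether feature values are levels or changes is left open, the repeated measures ANOVA cancels stable scanner offsets within a patient, and phantom scans are used to align the protocols. None of this puts centre into the dose model.

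Finally, the study calls itself exploratory, the test of change over time does use baseline, and prediction of decline rests on the NTCP models, which are also fitted per institution. This limits the weight of the point. It does not answer it, because section 7.2.1 itself fixes the covariate list rather than leaving it to a later plan.

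**Conclusion.** The point stands in limited form. The 1- and 2-year models as listed address current level, while the objective is decline, and this follows from the text without any assumption. The loss of precision is material: 25% to 49% of the residual variance, under an assumed r of 0.5 to 0.7. It does not depend on confounding. Bias is a risk of unknown size and should be described as such. Time since RT explains almost nothing within a visit, but it is a matter of definition, not of lost power. Centre is missing from both general linear models; scanner is a concern only for the imaging outcomes. This should be corrected, but it does not undermine the test of change over time.

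**What to change.** In section 7.2.1, add the baseline z-score of the same outcome and centre to the 1- and 2-year models. Alternatively, add dose and dose-by-time terms to the mixed model and make that the dose analysis. Define the starting point of time since treatment, or drop it. Fit a dose model at baseline only as a check for confounding: an association with a dose not yet given would show how far dose and pre-RT deficit go together.

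In section 7.2.2, add the baseline imaging value, tumour location and centre (which stands for scanner) to the general linear model of imaging features, and say whether the outcome is a level or a change.

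The cost is wording and a few degrees of freedom. In section 7.2.1 it is one for baseline and two for three centres, less one if time since treatment is dropped. No new data are needed.

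In reporting, present the baseline-adjusted dose coefficient as reducing confounding by pre-RT status, not as removing it.

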7.1 Sample size

Study subjects will be recruited from the radiation-oncology center of three centers: UZ Leuven, UZ Gent and Iridium Kankernetwerk Antwerpen. From a pragmatic perspective, we estimate to recruit 12-15 patients yearly in each of the three centers, resulting in 120 patients in three years in total.

Cognitive impairment has been reported in primary brain tumour patients and is roughly estimated to be present in about half of patients³⁹⁻⁴⁰. Although limited (good quality) evidence exists for our

type of study, power calculations were performed based on the two most extreme studies (i.e. one showing minimal amount of cognitive impairment⁴¹ and one showing maximal amount of cognitive impairment⁴². In both studies cognitive performance is assessed at baseline and about 12 months after radiotherapy in primary brain tumours. In the study by Moretti et al⁴², we used the cognitive outcome results of patients 9-12 months after radiotherapy (45-60 Gy), since the studied population will receive radiotherapy doses within this range. For power calculations, we used the performance on the digit span forward (processing speed) since the prevalence of impairment on this test was low (<20%). Based on these studies, effect sizes of d= 0,368 and d= 1,271 were found with a power of 0,800 and 0,868 respectively. This power would be 0,979 and 1,000 in our specific explorative study, in case of 120 inclusions. In order to detect this difference after 12 months with a power of 0.800 and a two-sided significance level α =0,05, the total required sample size would thus range between 8-60 patients. Power calculations were performed using Gpower 3.1⁴³.

Sample size calculation for the prediction models was performed using a recently developed software package⁴⁴. Since the event rate of cognitive impairment is unclear, we performed power calculations for the lowest and highest event rate, i.e. 0,2-0,5 (see above). When considering 4 candidate predictors and rMSPE of 0,1, the required sample sizes ranges between 90 and 120 patients respectively. Therefore, including 120 patients will allow building a sufficiently complex prediction model combining four dosimetric and/or clinical features.

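### Single-step Bonferroni over the five cognitive outcomes is valid, but Holm's step-down correction is uniformly at least as powerful at the same family-wise error: a cheap, low-severity improvement

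*Protocol*

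**What the plan says.** Section 7.2.1 models the neuropsychological and questionnaire scores: the effects of patient and treatment factors "will be investigated using general linear models (predictors= tumour location, radiation dose, covariates= gender, age at treatment, time since treatment and socio-economic status"), separately at each timepoint. The next sentence sets the multiplicity rule: "Bonferroni correction will be applied as" the "method for statistical correction of multiple tests, for each test outcome (n=5 outcomes; memory, executive functioning, attention, visuomotor function, working memory) that is predicted". No step-down form is named, and no reason is given for the single-step form. The section states no alpha of its own. Section 7.1 works "with a power of 0.800 and a two-sided significance level α =0,05", so 0.05 is taken here as the family-wise level, which makes the Bonferroni threshold 0.05/5 = 0.01 per outcome. The same section promises effect sizes (partial eta squared and Cohen's d) but no simultaneous confidence intervals.

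**The concern.** One of the two research questions in section 7.2.1 asks which cognitive domains are affected. For that question the relevant quantities are the power for each affected domain and the chance of finding all of them. The power to find at least one matters less. Single-step Bonferroni tests every domain at 0.01 even after others have been rejected. Holm relaxes the threshold after each rejection without giving up error control. If a predictor such as dose or tumour location acts on several domains, the plan will flag fewer of them than it could at the same error rate. What is at stake is lost power in a secondary set of models. No test becomes invalid.

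**Working it through.** **1. The plan's own power figures.** Section 7.1 reports "effect sizes of d= 0,368 and d= 1,271 were found with a power of 0,800 and 0,868 respectively", then "This power would be 0,979 and 1,000 in our specific explorative study, in case of 120 inclusions", and "the total required sample size would thus range between 8-60 patients". A paired t-test (exact noncentral t, two-sided 0.05) reproduces these:

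- d = 0.368: N = 60 (power 0.801), and power 0.979 at N = 120.
- d = 1.271: N = 8 (power 0.867, against 0.868 stated).

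These figures use an unadjusted 0.05. At 0.01 and d = 0.368, power at N = 120 is 0.919, and N for 80% power is 90. They concern within-patient change over 12 months, not the predictor models to which the correction is attached.

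**2. Why Holm dominates.** Order the five p-values. Holm compares them in turn with 0.05/5 = 0.01, 0.05/4 = 0.0125, 0.05/3 = 0.0167, 0.05/2 = 0.025 and 0.05, and stops at the first failure.

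- *Never fewer rejections.* Every threshold is at least 0.01. If a p-value is at most 0.01, so are all the smaller ones, so the procedure reaches it and rejects it.
- *Same error rate.* With k true null hypotheses, the first one that could be wrongly rejected is met while at least k hypotheses remain, so its threshold is at most 0.05/k. The sum over k nulls is at most 0.05, whatever the correlation.

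**3. Inputs for the size.** From the documents: five outcomes, n = 120, and partial eta squared 0.06 (section 7.2.1, moderate). Assumed, because the protocol does not give them: family-wise level 0.05, a 1-df test of one predictor, n − 10 residual df, equal effects in the affected domains, and outcome correlation 0.3 to 0.5.

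**4. Bonferroni power.** Noncentrality = √(n × η²/(1 − η²)).

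- n = 120: √(120 × 0.06/0.94) = √7.66 = 2.77. With 110 df and a two-sided 0.01 test (critical t = 2.62), power = 0.56.
- n = 100: √(100 × 0.06/0.94) = √6.38 = 2.53, power = 0.46.

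**5. Holm power.** Simulation of 120,000 sets of five correlated t statistics per scenario, η² = 0.06, n = 120:

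| Domains truly affected | Bonferroni, per affected domain | Holm, per affected domain |
|---|---|---|
| 1 | 0.56 | 0.56 |
| 2 | 0.56 | 0.58 |
| 3 | 0.56 | 0.60 |
| 5 | 0.56 | 0.66 to 0.67 |

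With all five affected, the chance of finding all five goes from 0.14–0.21 to 0.37–0.45. With 100 evaluable patients and five affected, power per domain goes from 0.46 to 0.55–0.56. Holm's simulated family-wise error was below 0.05 in every scenario, and Holm rejected everything that Bonferroni rejected.

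**6. Other effect sizes.** With three affected domains at n = 120, the plan's weak label (0.03) gives 0.25 to 0.27 and its large label (0.14) gives 0.96 to 0.97. Both gains are smaller than the 0.04 at the moderate label. Carrying over d = 0.368 from section 7.1 (normal approximation, N = 120, correlation 0 to 0.5), power per domain goes from 0.93 to 0.93 with one affected domain, 0.95 with three and 0.97–0.98 with five. The power to reject at least one hypothesis is essentially unchanged throughout.

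**The case against.** The case for leaving the text alone has several parts.

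- *Bonferroni is correct.* It controls the family-wise error, and section 7.2.1 is not inconsistent. This stands: the point is about efficiency.
- *The analysis is peripheral.* The primary objective is the NTCP model (sections 3.1 and 7.2.4), which rests on penalised logistic regression, AUC and bootstrapping and is not touched by this correction. The background section calls the study exploratory. This stands and keeps the severity low.
- *The gain may be small.* The background links hippocampal dose to memory and frontal dose to executive functioning. For a structure-specific dose that suggests few affected domains per predictor, where Holm adds little or nothing. The moderate label is only a guide to interpretation, and a multi-level tumour location factor would not be a 1-df test (with 3 df, Bonferroni power is about 0.37). All of this stands as a limit on the size.
- *The edit is more than one word.* Holm must rank a defined set of p-values. The table in section 5.2 lists several tests for some domains (four for memory, two for executive functioning), and section 7.2.1 standardises each test without defining a domain composite. This stands and is taken up in the fix.
- *Bonferroni gives simple simultaneous intervals.* True, but the plan promises effect sizes and no such intervals, so this carries little weight.

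A reader might go further and infer that a domain missed under Bonferroni is a wrong answer to the trial's own question. The documents do not support that: effect sizes are reported regardless of significance, and nowhere is a non-significant domain declared unaffected.

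**Conclusion.** The point holds as a low-severity improvement. On the same five p-values Holm is never worse than the planned correction and needs no further assumption. The benefit runs from nil with one affected domain to about 10 percentage points per domain with all five, at n = 120 and η² = 0.06. Two to three affected domains give 2 to 4 points. These sizes rest on the assumed family-wise level, 1-df test, correlation and equal effects, and on an effect-size label that the plan never used for planning. It would be tempting to quote the five-domain figure as the expected gain, but it is the best case, and the protocol does not say how many domains a predictor should affect. Nor does the point show an error in the plan or a weakness in the primary NTCP analysis.

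**What to change.** In section 7.2.1, replace the Bonferroni correction by the Holm step-down (Holm–Bonferroni) correction. Apply it for each predictor at each timepoint, over the same five outcome p-values that would otherwise have been compared with 0.05/5. State the family-wise level. Where a domain has several tests, state which p-value represents it. Report Holm-adjusted p-values next to the effect sizes already promised.

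The change needs no new data or patients. Its cost is a few sentences of text, mainly to define the p-value for each domain, and the loss of simple matching simultaneous confidence intervals; unadjusted intervals, labelled as such, can stand beside the adjusted p-values. Multiplicity across predictors, timepoints and questionnaire scores stays unaddressed, as it is now.
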